In a current study (UAMS IRB #206164; Co-I: [name]), we have enrolled lean and obese subjects in a very narrow age range (5-9 years of age) in order to control for pubertal state. Bioenergetic profiling using the Seahorse XF96 Analyzer (Seahorse Bioscience, Inc., North Billerica, MA), a core ACRI equipment, is routinely performed by [name]⁻⁴⁰. The Seahorse measures oxygen consumption rate (OCR) and extracellular acidification rate (ECAR) in a 96-well plate of intact living cells. The sequential injection of up to four compounds into each well enables the interrogation of bioenergetics in real-time. **Figure 2A and B** presents the ATP Production Rate Assay on PBMC from lean, obese and T2D children enrolled in an ongoing study (UAMS IRB #206164; Co-I: [name]). In this assay, basal OCR and ECAR are initially measured, followed by the injection of oligomycin (oligo), an ATP synthase inhibitor, to block ATP production by the mitochondrial electron transport chain (ETC) and induce compensatory glycolysis. Next, antimycin A (AMA) and rotenone (ROT), inhibitors of ETC complex III & I, respectively, are injected together. Shutting down the ETC allows for calculating the amount of media acidification (ECAR) that was due to CO₂ production during OXPHOS. Proton efflux rate (PER) is calculated post-assay from ECAR and the buffering capacity of the assay media, and finally, validated calculations derive ATP generated by OXPHOS (mitoATP) and by glycolysis (glycoATP)⁴¹, which is presented in **Figure 2C**. **Figure 2D** shows that the % ATP derived from glycolysis is significantly greater in PBMC in the T2D group as compared to the OB group ($p=0.032$). While no differences between the lean and obese group are observed in this preliminary data, the increased % glycolysis in the T2D group supports the notion that obese children with metabolic dysfunction have more pro-inflammatory cells and fewer T_{regs} in circulation. There are several important points to

[figure not shown]

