1. Anthropometrics: Anthropometric measurements including height, weight, waist circumference, hip circumference, blood pressure, and pulse will be obtained using standardized techniques. BMI-for-age will be calculated and plotted on CDC growth charts to confirm lean/obese stratification.
2. Tanner (Puberty) Stage Assessment: Parents will be asked to complete a form with drawings depicting pubertal development. This form is used to determine pubertal status. The questionnaire given to parents to complete is subjective and a parent could potentially incorrectly assess Tanner Stage. Because the results from the samples may be influenced by the participant's pubertal development, pubertal development must be accounted for. At the beginning stages of puberty, insulin levels rise dramatically showing insulin resistance. Thus, if the study determines the child to have insulin resistance but insulin resistance is actually due to development of puberty instead of being metabolically unhealthy then this could alter the results and conclusions made from the study. Because of this, it is important to the study and the results to have the correct Tanner Stage level for each participant. In order to validate the parent's assessment of Tanner Stage level, hormone tests may be conducted on the blood sample obtained.
3. Physical Activity Questionnaire (Elementary School): A parent or participant will complete a form indicating the level of physical activity the participant had during the previous week in order to provide general estimates of physical activity levels for each subject during a 7-day period prior to the study. In addition, the parent or participant will be asked about the participant's physical activity from the previous months leading up to the study visit.
4. Depression Scale: With assistance from the parent, a child will complete a form (Center for Epidemiological Studies Depression Scale for Children (CES-DC)) used as a depression scale. This scale will be used to account for depression as a confounding factor that could affect oxidative and bioenergetics parameters.
5. Body composition may be assessed by bioelectrical impedance analysis using the Tanita Body Composition Analyzer. A device (InBody 570 Body Composition Analyzer) similar to the Tanita, is routinely used in the clinic. The Tanita requires participants to stand still with bare feet on the weighing platform while a small amount of electrical current is used to measure impedance.

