- Taking any of the following medications that can affect study outcome: antipsychotics, thyroid hormone replacement therapy, inhaled/oral steroids, insulin, anabolic drugs (growth hormone replacement therapy and oxandrolone) and stimulants
- Taking metformin prescribed as part of their clinical care for longer than 3 weeks at the time of enrollment (may begin metformin therapy prescribed as part of their clinical care while enrolled in the study)
- BMI<5th percentile for age/sex (classified as underweight based on CDC growth charts)
- Subjects determined ineligible by the PI or delegated staff.

Recruitment:

Study investigators, research staff, or any qualified personnel will conduct recruitment of study participants using IRB approved advertisements and methods.

We will recruit some subjects who agreed to be contacted for future research from an ongoing human research study, Bioenergetics and Metabolism in Pediatric Populations (BMPP; UAMS IRB #206164; [name] and [name], Co-PIs). In the BMPP study, we have enrolled 55 children in a period of 1 year and thus, we do not anticipate difficulty meeting this recruitment goal as the recruitment criteria are relaxed, with a wider age range, for the proposed study.

Advertisements may be distributed in the form of postcards or flyers via direct mail, at information booths or events, or to various locations for posting or distributing, including pediatricians' offices, health fairs, daycare centers, schools/universities, recreational centers, grocery stores, supermarkets, child retail stores, websites (ACH, ACRI, ACNC, UAMS, and others as applicable), and churches. Also, print or digital ads may appear in newspapers, magazines, social media, newsletters, and circulars. On-hold phone messages, BoomText messages, screensavers, and radio/television advertisements may be used. In addition, research staff may contact parents who expressed an interest in our studies or who previously agreed to be contacted regarding future studies. Research staff may also contact parents who have signed up for the AC research registry. The research staff will educate the parents and children about the study and if interested determine potential eligibility. At the visit, study staff would obtain informed consent in person.

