Prior to any analyses, endpoints data for each group will be closely inspected for the potential presence of unusual values; effort will be made to conserve all data. Analyses will be carried out in SAS 9.4 (SAS Institute, Cary NC) at the 5% significance level; point and 95% interval estimates will be obtained for relevant metabolic group comparisons. Parametric techniques will be first choice and nonparametric equivalents if assumptions are not met. Special attention will be paid to unequal variances.

The study planned four groups of children: lean, healthy obese/overweight, insulin-resistant obese/overweight, and overweight/obese with T2D. Primary comparison of interest are these three: the average of insulin-resistant and T2D obese children compared to (i) lean children and (ii) healthy obese children; and (iii) lean children compared to healthy obese children. Outcomes important to this aim are proportions of T_{reg} cells among circulating CD4 $^{+}$ T cells and CD4 $^{+}$ T glycoATP and mitoATP production. Initially, we will use a one-factor ANOVA to analyze these outcomes (possibly with suitable transformations). Comparisons of interest will then be made with 0.05 significance level *t*-tests conducted within the ANOVA framework.

The requested sample sizes will provide about 0.80 power for detecting differences in means of size 0.8 SD for comparisons (i) and (ii) and size 0.9 SD for comparison (iii), where SD is the within-group standard deviation (a.k.a., root mean square error from the ANOVA). For proportions of T_{reg} cells – a primary outcome of interest, an estimate of the SD is 2.3 percentage points (ref Table 1 of Arismendi et al.⁴²). So, if the means differ by at least 1.85 percentage points in comparisons (i) & (ii) and by 2.10 percentage points for comparison (iii), we will be able to detect these differences with a reasonably high probability (0.80 or higher).

Ethical Considerations

This study will be conducted in accordance with all applicable government regulations and University of Arkansas for Medical Sciences research policies and procedures. This protocol and any amendments will be submitted and approved by the UAMS Institutional Review Board (IRB) to conduct the study.

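### Puberty has to be accounted for, the protocol says, but no rule states how Tanner stage enters the primary analysis or the insulin-resistant split

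*Combined protocol and SAP*

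**What the plan says.** Data Analysis defines four groups (lean, healthy overweight/obese, insulin-resistant overweight/obese, and T2D) and three primary comparisons: the average of the insulin-resistant and T2D groups against lean (i) and against healthy obese (ii), and lean against healthy obese (iii). The outcomes are the Treg proportion, glycoATP and mitoATP. On the model it says: "Initially, we will use a one-factor ANOVA to analyze these outcomes (possibly with suitable transformations". The comparisons are then t-tests at the 0.05 level inside that ANOVA. No covariate, stratum or sensitivity analysis is named.

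Study Procedures, item 2 (Tanner stage), says: "Because the results from the samples may be influenced by the participant's pubertal development, pubertal development must be accounted for". It gives the reason: "At the beginning stages of puberty, insulin levels rise dramatically showing insulin resistance". The next sentence opens "Thus, if the study determines the child to have insulin resistance but insulin resistance is actually due to development of puberty" and goes on to say that results and conclusions could be altered. Stage comes from a form filled in by the parent. Item 2 warns: "The questionnaire given to parents to complete is subjective and a parent could potentially incorrectly assess Tanner Stage". As a check it says that "hormone tests may be conducted on the blood sample obtained".

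Preliminary Data reports that a current study enrolled children in a "very narrow age range (5-9 years of age) in order to control for pubertal state". Recruitment says that "the recruitment criteria are relaxed, with a wider age range, for the proposed study", and Study Population sets the range at 5 to 17 years. Preliminary Data also plans to match groups on age and to divide obese children by insulin sensitivity. Study Population makes balance on age, sex and ethnicity an aim. Neither mentions Tanner stage.

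**The concern.** The protocol sets itself a requirement and the analysis section does not carry it out. The groups are not randomised. Children of the same age can differ in Tanner stage, and by item 2's own reasoning a split on insulin sensitivity can sort same-age obese children by puberty. Comparisons (i) and (ii) use the insulin-resistant group, and (ii) and (iii) use the healthy obese group left by the same split, so all three are exposed.

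If the pubertal mix differs between groups and puberty affects Treg or ATP outcomes, part of that difference would be reported as an effect of metabolic group. If puberty acts the other way, a real difference would be hidden. Neither the p-value nor the 95% interval would show it.

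**Working it through.** **1. The plan's own power.** Inputs from Study Population and Data Analysis: about 20 children per group; detectable differences 0.8 SD for (i) and (ii) and 0.9 SD for (iii); SD 2.3 percentage points for Treg. Two-sided 0.05 is assumed, since sidedness is not stated. Error df = 80 − 4 = 76.

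- (i), (ii): variance = 1/20 + 0.25/20 + 0.25/20 = 0.075 SD², SE = 0.274 SD, noncentrality 0.8/0.274 = 2.92, power 0.822.
- (iii): variance = 1/20 + 1/20 = 0.10 SD², SE = 0.316 SD, noncentrality 0.9/0.316 = 2.85, power 0.802.

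Both agree with the stated figure of about 0.80. That figure contains no puberty term.

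**2. Type I error of the unadjusted contrast.** The documents give neither a puberty effect nor the proportion pubertal by group, so these inputs are assumptions. Bias = puberty effect × difference in proportion pubertal. Type I error is the two-sided noncentral t probability (df 76) with noncentrality bias/SE.

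| Difference in proportion pubertal | Puberty effect (SD) | Bias (SD) | Bias (Treg points, × 2.3) | Type I, (i)/(ii) | Type I, (iii) |
|---|---|---|---|---|---|
| 0 | any | 0 | 0 | 0.050 | 0.050 |
| 0.15 | 0.25 | 0.0375 | 0.09 | 0.052 | 0.052 |
| 0.15 | 0.75 | 0.1125 | 0.26 | 0.069 | 0.064 |
| 0.30 | 0.25 | 0.075 | 0.17 | 0.058 | 0.056 |
| 0.30 | 0.75 | 0.225 | 0.52 | 0.128 | 0.108 |

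For scale, the plan's detectable Treg difference for (i) and (ii) is 1.85 points. If the bias opposes a true effect, power uses (0.8 or 0.9 − bias)/SE. For (i)/(ii) it falls from 0.822 to 0.698–0.785 at a difference of 0.15 and 0.545–0.743 at 0.3. For (iii) it falls from 0.802 to 0.691–0.768 and 0.559–0.731.

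**3. How large a difference in proportion pubertal is that?** Assume ages uniform from 5 to 18 in every group, with stage set by age plus noise of SD 1, 2 or 3 years. Without any advance, 0.56 of each group is pubertal. A 2-year pubertal advance raises this to 0.70–0.71 (difference about 0.15), and a 4-year advance to 0.82–0.87 (about 0.3). A 1-year advance gives about 0.08. With matched groups aged 10–18, a 2-year advance gives only 0.10–0.12.

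**4. Power after adjustment.** With one binary puberty term, variance = Σc²/20 + (Σcp)²/(20 Σp(1−p)), df 75, where c is the contrast weight and p the proportion pubertal. No puberty effect is assumed, so nothing is gained back in residual variance.

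- Balanced: 0.822 for (i)/(ii) and 0.802 for (iii).
- p = 0.55, 0.55, 0.85, 0.85 (lean, healthy obese, insulin-resistant, T2D): variance for (i)/(ii) = 0.075 + 0.09/15 = 0.081, power 0.79.
- p = 0.55, 0.85, 0.85, 0.85: variance for (iii) = 0.10 + 0.09/12.6 = 0.107, power 0.775.

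With three-level Tanner stage, age and sex together (df 72, simulated designs as in step 3, puberty effect 0 to 0.75 SD):

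| Difference in proportion pubertal | Power, (i)/(ii) at 0.8 SD | Power, (iii) at 0.9 SD |
|---|---|---|
| 0 | 0.80–0.86 | 0.78–0.84 |
| 0.15 | 0.76–0.84 | 0.75–0.82 |
| 0.30 | 0.66–0.79 | 0.68–0.77 |

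The low ends assume no puberty effect. The loss comes from the overlap of Tanner stage with age and group.

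**The case against.** A reader might infer that widening the age range removed all control of puberty. The documents do not support that: they plan age matching, aim for balance on age, sex and ethnicity, collect Tanner stage and allow hormone checks. Item 2 also ties correct staging to judging whether insulin resistance is pubertal, so stage has an intended role. What is missing is the rule that puts it to use.

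A reader might also take the Tanner form as optional, because Study Design and Procedures says the visit may include it. That wording covers the blood draw as well. The form stands in the list of procedures for each visit and among the procedures to be completed at the research site before compensation. Only urine and stool are labelled optional.

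The sizes rest on assumptions, and the largest need a pubertal advance of about 4 years between age-matched groups. At 0.15, inflation is small. This stands.

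Adjustment is also imperfect, and this stands too. It does not correct children labelled insulin resistant because of puberty, which is item 2's main worry. If obesity itself brings puberty forward, Tanner stage lies on the pathway for (i) and (iii), and adjusting changes what is estimated.

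Finally, the study is observational and meant as preliminary data for a grant application, and describing the ANOVA as the initial step leaves room for later models. But none is named, and a model chosen after seeing the data is a weak answer to a stated requirement.

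**Conclusion.** The point holds as a gap between a stated requirement and the analysis plan, and closing it is a cheap improvement. Under assumed puberty effects of 0.25 to 0.75 SD, the nominal 0.05 test runs at 0.052–0.069 for (i)/(ii) and 0.052–0.064 for (iii) at a 0.15 difference in proportion pubertal. At 0.3 it runs at 0.058–0.128 and 0.056–0.108. If puberty is balanced or has no effect, the unadjusted test is valid.

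Two stronger readings should be resisted. The documents do not show that the comparisons will be biased, since they give no puberty effect or imbalance, and 0.128 is the corner of an assumed range. Nor is the power statement wrong: it reproduces for the unadjusted analysis.

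**What to change.** In Data Analysis:

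1. Prespecify that (i) to (iii) are estimated, with 95% intervals, from a model with four-level group plus Tanner stage, its grouping fixed before analysis. Add age and sex if that grouping leaves them estimable. Report the unadjusted one-factor ANOVA alongside.
2. State that for (i) and (iii) the adjusted contrast leaves out any part of an obesity effect that acts through earlier puberty, which is why both estimates are shown.
3. State how Tanner stage is used in the healthy versus insulin-resistant split. Because adjustment cannot correct children misplaced by puberty, add a sensitivity analysis in the non-T2D overweight/obese children that uses a continuous fasting insulin/glucose measure plus Tanner stage.
4. Report Tanner stage by group.
5. Describe the 0.80 power as applying to the unadjusted or balanced case.

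The cost is a text amendment through the IRB. The Tanner form, insulin and glucose are already listed procedures. Power for (i)/(ii) stays near 0.79–0.82 with a single binary puberty term at differences up to 0.3, but may fall to about 0.66–0.79 with Tanner stage and age together under strong imbalance. Misreported stage leaves part of the bias: in simulations with 20% of children one stage out, adjustment removed roughly 35% to 59% of it for (i).

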Figure 2: The ATP production rate assay demonstrates increased % glycolysis-derived ATP production in PBMC from T2D children. Oxygen consumption rate (OCR) (A) and Proton Efflux Rate (PER) (B) are plotted over time in PBMCs from lean, obese (OB) and type 2 diabetic (T2D) children. Injections of Oligomycin (oligo) and Antimycin A (AMA) and Rotenone (ROT) are indicated. (C) Glycolytic ATP production rate (glycoATP) and mitochondrial ATP production rate (mitoATP) are calculated from OCR and PER. (D) % glycolysis and % OXPHOS-derived ATP production are calculated. * $p=0.032$

Methods: Freshly isolated PBMC from lean ($n=8$), obese (OB; $n=11$), and treatment-naive type 2 diabetic (T2D; $n=2$) children were plated at 2.5×10^6 cells/well in RPMI 1640 with 1mM HEPES, 2mM glutamine, 1mM pyruvate and 11mM glucose on poly-D-lysine coated XF96 plates. Plates were centrifuged at 100xg with no brake to adhere cells to well bottoms. After a 30 min incubation in a 37°C non-CO₂ incubator, cells were assayed in a Seahorse XF96.

note regarding this data: 1) these data are from PBMC, a mixed population of cells including monocytes and lymphocytes of various subtypes rather than purified CD4⁺ T cells as proposed in this study; 2) the obese subjects have not been classified as metabolically healthy or unhealthy; 3) the age of the T2D subjects is greater (16.5±0.1 years; mean±SD) than the other groups (lean: 6.8±1.1 years; obese: 7.9±1.4 years). In the studies proposed herein, we will match groups on age and subgroup obese subjects as metabolically healthy and unhealthy based on insulin sensitivity. Further, after measuring high sensitivity CRP (hsCRP), we will compare subjects with hsCRP values in the top quartile to the other groups to determine whether the % glycolysis is higher in CD4⁺T cells from those obese subjects with inflammation.

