A prospective subject and his/her parent or legally authorized representative will come for the study visit that will last up to 2.5 hours depending on the duration of the consenting process and blood draw. A subject (and/or his/her parent) will be provided a questionnaire regarding the subject's medical history that will be reviewed by study staff to identify patients who fulfill inclusion/exclusion criteria. In addition, study staff may review medical records from ACH or other healthcare practitioners (such as physicians or pharmacists) outside ACH in order to confirm the inclusion/exclusion criteria. Information from medical

Title: Immunometabolism in Pediatric Obesity

PI: [name].

records may be collected from the time of consent up until the time that data analysis for this study is complete and results have been published. Study staff will ask parents about demographic information including biologic gender, date of birth, race/ethnicity, and parental occupations as well as grade in school.

Prior to the study visit, study staff may contact the parent and ask questions relating to inclusion/exclusion criteria, for medications that the participant is currently taking and may ask of any new health diagnoses. In the event that the participant is taking medications or has a new health diagnosis that may cause him/her to be ineligible to participate in the study visit, the study visit may be rescheduled or canceled. Study staff may contact a parent and send the IRB approved consent form and information regarding the scheduled visit to the parent(s) prior to the scheduled date. If the consent form is revised prior to the scheduled visit, the new IRB approved consent form may be sent to parents. If applicable, the parent will be informed of the blood draw and advised that if the parent wishes their child to complete the blood draw at the visit, the child will need to have not taken seasonal allergy medication (e.g. Claritin) in the prior 72 hours and will need to be fasting including no food or liquid after 12 am, except for water and medications the day of the visit.

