to complete the procedure(s). At the first, second, or reattempt visits, participants/parents may be given up to \$20 in ACRI merchandise and/or child-friendly stickers. Food and drinks may be provided during study visits following the fasting blood draw.

Study Population

110 children ages 5-17 years old will be recruited with the goal that approximately 80 subjects stratified across the following groups will complete the study: i) healthy lean (approximately n=20); ii) overweight/obese (approximately n=40, with the anticipation that approximately 20 of these children will be insulin resistant); iii) overweight/obese with T2D and prescribed Metformin (approximately n=20). Every attempt will be made to ensure that the desired number for each group is achieved and groups are balanced with respect to age, sex and ethnicity.

Inclusion Criteria:

- Age 5-17 years, inclusive
- Either healthy lean ($BMI \geq 5^{\text{th}}$ percentile and $< 85^{\text{th}}$ percentile for age/sex) or overweight ($BMI \geq 85^{\text{th}}$ percentile and $< 95^{\text{th}}$) or obese ($BMI \geq 95^{\text{th}}$ percentile for age/sex)
- For those with $BMI \geq 85^{\text{th}}$ percentile for age/sex, parental verbal confirmation that the child had a history of $BMI \geq 85^{\text{th}}$ percentile for age/sex for at least six months prior to study enrollment

OR

- Age 5 years - 17 years 5 months, inclusive
- Either overweight or obese ($BMI \geq 85^{\text{th}}$ percentile for age/sex)
- Parental verbal confirmation that the child had a history of $BMI \geq 85^{\text{th}}$ percentile for age/sex for at least six months prior to study enrollment
- Diagnosed with type 2 diabetes mellitus or insulin resistance
- Prescribed metformin (either not yet taking or began taking within 3 weeks of enrollment)

Exclusion criteria:

- Having an infection (viral, respiratory, gastrointestinal) in the previous 4 weeks
- Genetic or physical conditions impacting mobility over past year as determined by the PI
- Having known chronic illnesses/disorders that may independently affect study outcome measures: type 1 diabetes mellitus, neurologic (e.g. epilepsy), developmental (developmental delay, autism spectrum disorder), endocrine (thyroid, Cushing's), hepatic, autoimmune, cardiac and renal disorders. Also, chronic lung disorders except well controlled asthma that does not require permanent use of inhaled/oral steroids

Title: Immunometabolism in Pediatric Obesity

PI: [name].

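### The groups are not randomised and balance on age, sex and ethnicity is only an aim, yet the one stated model adjusts for none of these, nor for pubertal stage

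*Combined protocol and SAP*

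**What the plan says.** The Study Population section undertakes to try to ensure that "groups are balanced with respect to age, sex and ethnicity". It gives no quota or matching procedure for sex or ethnicity. The Preliminary Data section adds, for age, that "we will match groups on age and subgroup obese subjects as metabolically healthy and unhealthy based on insulin sensitivity". Under Study Design and Procedures, staff collect "demographic information including biologic gender, date of birth, race/ethnicity". The Tanner stage item in the same section says that puberty can influence the results and has to be accounted for. The depression scale item gives confounding as the reason for collecting that scale.

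The Data Analysis section then states: "Initially, we will use a one-factor ANOVA to analyze these outcomes (possibly with suitable transformations". It continues: "Comparisons of interest will then be made with 0.05 significance level", by t-tests within that ANOVA. The first two contrasts use "the average of insulin-resistant and T2D obese children compared to (i) lean children and (ii) healthy obese children". The third sets the lean group against the overweight/obese group without insulin resistance. No covariate, adjusted model or sensitivity analysis is named.

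**The concern.** The protocol names factors on which the groups should be comparable, collects the data on them, and then has no analysis that uses them. Randomisation offers no protection in a cross-sectional comparison. Two features make balance hard to secure by recruitment. The T2D group depends on which children are newly prescribed metformin. The split of the overweight/obese children into healthy and insulin resistant is anticipated at about 20 each, and it rests on insulin sensitivity.

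If the groups differ systematically in age, pubertal stage, sex or ethnicity, and that factor is related to Treg proportion, glycoATP or mitoATP, the difference enters the unadjusted contrast and can be read as an effect of obesity or metabolic state. Without a prespecified adjusted model, any adjustment would be chosen after the imbalance, and perhaps the results, had been seen.

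**Working it through.** **Inputs from the documents.** Four groups of about 20: lean, healthy overweight/obese, insulin resistant, T2D (Study Population). Detectable differences of 0.8 SD for (i) and (ii) and 0.9 SD for (iii), power about 0.80, Treg SD 2.3 percentage points (Data Analysis). Two-sided tests are assumed, since sidedness is not stated.

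**The plan's own figure.** Error df = 80 − 4 = 76.
- SE for (i) and (ii) = SD × √(1/20 + 1/40) = 0.274 SD. Noncentral t power at 0.8 SD = 0.822.
- SE for (iii) = SD × √(2/20) = 0.316 SD. Power at 0.9 SD = 0.802.

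The stated power of about 0.80 therefore reproduces for the unadjusted model. On the Treg scale, 0.8 × 2.3 = 1.84 and 0.9 × 2.3 = 2.07 points, against the stated 1.85 and 2.10.

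**Bias from an imbalance that remains.** Bias = covariate effect (in SD) × difference in the covariate's share. The documents give no covariate effect, so a range is assumed. The rejection rates hold given the gap shown.

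| Assumed effect × gap | Bias, SD | Bias, Treg points | Rejection under the null, (i) | (iii) |
|---|---|---|---|---|
| 0 × any | 0 | 0 | 0.050 | 0.050 |
| 0.3 SD × 20 points | 0.06 | 0.14 | 0.055 | 0.054 |
| 0.5 SD × 20 points | 0.10 | 0.23 | 0.065 | 0.061 |
| 0.5 SD × 30 points | 0.15 | 0.35 | 0.084 | 0.075 |
| 0.8 SD × 40 points | 0.32 | 0.74 | 0.211 | 0.170 |

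If a bias of 0.10 to 0.15 SD runs against a true effect of the planned size, power for (i) falls from 0.822 to between 0.714 and 0.649.

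**How large a gap chance alone would give.** Take sex with a 50/50 mix in every group. The SD of the difference in share is √(0.25 × (1/20 + 1/40)) = 0.137 for (i) and (ii), and √(0.25 × 2/20) = 0.158 for (iii). From the exact binomial distribution, a gap of at least 20 points has probability 0.17 in (i) and 0.27 in (iii). A gap of at least 30 points has probability 0.035 and 0.08.

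**What chance imbalance does to type I error overall.** In 200,000 simulated trials with equal sex mixes and no group effect, the one-factor test of (i) rejected in about 5% of runs, with a sex effect of 0.5 SD and also with 0.8 SD. The sex variation is already in the error term, so the test keeps its level on average.

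**Power after adjustment.** Assume 4 covariate df (for example sex 1, ethnicity in three categories 2, age 1), so error df = 72. The SE is multiplied by √(1 − R²), where R² is the share of within-group variance explained (assumed). Ordinary chance imbalance multiplies the variance by about 1 + 4/71. Power for (i) at 0.8 SD, against 0.822 unadjusted:

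| R² | Balanced | Ordinary chance imbalance |
|---|---|---|
| 0 | 0.822 | 0.801 |
| 0.05 | 0.841 | 0.820 |
| 0.10 | 0.859 | 0.840 |
| 0.15 | 0.878 | 0.860 |

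A balanced 50/50 factor with a 0.5 SD effect explains about 0.25 × 0.5² = 6% of the variance, so an R² of 0.10 to 0.15 needs more than one such factor.

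**The case against.** A reader might infer that leaving the factors out biases all three comparisons and wastes precision as a matter of course. The documents do not support that. Both effects need the factor to be related to the outcomes, and no section says that sex or ethnicity is. Bias in a given contrast also needs imbalance in that contrast.

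A reader might also take 0.084 as the real type I error of the plan. It is the rate given a fixed 30-point gap and an assumed 0.5 SD effect. By chance alone a gap that large is uncommon in (i), and chance imbalance leaves the overall error at 5%.

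Nor are the unadjusted intervals too wide in any sense that breaks a promise. They have correct coverage when the groups are balanced, and the power statement was made for this model. If the covariates explain nothing, adjustment costs a little power.

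The documents also support some covariates better than others. Sex and ethnicity appear only as balancing aims. Age is in the same sentence and is also to be matched, and puberty and depression are described in terms of accounting or confounding. An adjusted model limited to sex and ethnicity would miss the better-supported factors.

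All of this stands, and it limits the size and widens the remedy. The last argument, that the word Initially leaves room for a later model, does not rescue the plan: no such model is described, and the three comparisons are tied to this ANOVA.

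**Conclusion.** The point holds as a conditional weakness that is cheap to remove. The plan relies on recruitment alone to make non-randomised groups comparable and has no prespecified analysis if that fails. The risk is systematic imbalance, not chance imbalance. For an assumed 0.5 SD effect and a gap of 20 to 30 points in share, the illustration gives a bias of 0.10 to 0.15 SD and a conditional rejection rate for (i) of 0.065 to 0.084. It could be nil if the factor is unrelated to the outcome, and larger if both the effect and the gap are large. The documents do not allow the actual size to be stated. The stated power is sound for the model it describes. These figures rest on two-sided tests, exact groups of 20, and the assumed effects, gaps and R² values.

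**What to change.** In the Data Analysis section, prespecify a linear model with group, sex, ethnicity, and age or pubertal stage. Choose between age and pubertal stage, and collapse ethnicity to a few named categories, before analysis; the documents define no categories, and cells in groups of 20 may be sparse. Estimate (i) to (iii) as contrasts of the adjusted group means, and report the one-factor ANOVA beside them as a sensitivity analysis. State whether the depression score enters the model, since the protocol collects it as a confounder.

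The cost is a few lines of text, no new data, and about 4 of 76 error df with sex, three ethnicity categories and age; a depression term would add to that. With ordinary chance imbalance and 4 df, power for (i) falls by about 2 points if the covariates explain nothing (0.822 to about 0.80). It rises by about 2 to 4 points if they explain 10 to 15% of within-group variance, or by about 4 to 6 points if the groups are balanced.
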